Total bilirubin (TBIL) $\leq 1.5 \times \text{ULN}$ ($\leq 3.0 \times \text{ULN}$ for patients with Gilbert's syndrome or liver metastases);

Aspartate aminotransferase (AST), alanine aminotransferase (ALT) and alkaline phosphatase (ALP) $\leq 3 \times \text{ULN}$, patients with confirmed liver or bone metastases must meet the following criteria:

Patients with confirmed liver metastases: AST and ALT $\leq 5 \times \text{ULN}$;

Patients with confirmed bone metastases: ALP $\leq 5 \times \text{ULN}$;

Serum albumin $\geq 2.8 \text{ g/dL}$;

d) Coagulation function

International normalized ratio (INR) or prothrombin time (PT) and activated partial thromboplastin time (aPTT) $\leq 1.5 \times \text{ULN}$;

Note: For patients with injectable lesions in the skin and/or subcutaneous tissue who are receiving anticoagulant therapy, prolonged INR, PT and aPTT are allowed, as bleeding can be controlled by direct pressure application, as determined by the investigator.

For female patients of childbearing potential (WOCBP), a negative pregnancy test result must be obtained within 7 days prior to the first dose of the study drug, and they must agree to use highly effective contraception or abstinence during the study drug treatment and for 6 months after the end of study drug treatment. In addition, female patients must be non-lactating and agree not to donate eggs during this period;

Note: WOCBP is defined as a female who has experienced menarche but has not

undergone surgical sterilization (hysterectomy or bilateral oophorectomy) or is not post-menopausal. Post-menopausal is defined as a female over the age of 45 years who has not had menses for 12 consecutive months in the absence of other biological or physiological causes. Additionally, females 55 years of age or younger must have a serum follicle-stimulating hormone (FSH) level >40 mIU/mL to be considered post-menopausal.

Hormone replacement therapy (HRT) may artificially suppress a woman's FSH levels and may require a washout period before the physiological FSH level can be restored. The duration of the washout period depends on the type of HRT. The following washout period durations are suggested as guidance, and the investigator should use their judgment based on the FSH level test results:

At least 1 week for vaginal hormonal products (rings, creams, gels);

At least 4 weeks for transdermal products;

At least 8 weeks for oral products;

Up to 6 months for other non-oral, non-transdermal products.

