Study Design: This is an open-label, dose-escalation Phase I clinical study conducted in patients with advanced solid tumors, aiming to evaluate the safety, tolerability, PK/PD characteristics, and preliminary efficacy of CNSI-Fe intratumoral injection in patients with advanced solid tumors.

Study Period: The study includes a screening period, a treatment period (including DLT evaluation period), and a follow-up period.

Screening Period: -28 to -1 days, to confirm that the subjects meet the inclusion criteria and do not meet the exclusion criteria.

Treatment Period (including DLT Evaluation Period): The DLT evaluation period is the first treatment cycle (duration: 21 days). During the DLT evaluation period, all subjects will receive CNSI-Fe intratumoral injection according to the protocol plan (preferentially selecting 1 suitable lesion for injection, tentatively with 1 injection on Day 1; if the corresponding dose of the investigational drug cannot be completed in 1 lesion, other lesions can be injected simultaneously; the dosing regimen may be adjusted by the sponsor and investigator based on the PK characteristics of this study). Safety assessments will be performed on Day 7, Day 14, and Day 21 after the first dose to evaluate DLT.

After the DLT evaluation is completed, subjects who do not experience unacceptable toxicity, if the investigator judges that the benefit of continued treatment outweighs

the risk, will enter the maintenance treatment period. In the maintenance treatment period, subjects will continue to receive one more dose of the investigational drug according to the DLT evaluation period dosing regimen (injection into the same lesion as the DLT evaluation period, tentatively with 1 injection on Day 1, the dosing regimen may be adjusted by the sponsor and investigator based on the PK characteristics of this study), and safety assessments will be performed on Day 7, Day 14, and Day 21 after dosing. Samples will be collected at the predetermined timepoints according to the study flow chart.

Follow-up Period: Safety follow-up until 28 days after the last dose.

Dose Escalation

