Note: Unless otherwise specified, all assessments, examinations, and sample collections should be performed on the same day before drug administration.

Screening Period: Routine examinations or examination results obtained at a tertiary hospital (or this hospital) within 28 days prior to the first dose (unless otherwise specified) and before signing the informed consent form (ICF) can be used for screening, and do not need to be repeated.

Treatment Period (DLT Evaluation Period): For the first intratumoral injection of CNSI-Fe, safety assessments will be performed on Day 7 (± 1 day), Day 14 (± 1 day), and Day 21 (± 1 day) after the first dose to evaluate DLT.

Maintenance Treatment Period: After the DLT evaluation is completed, subjects without unacceptable toxicity will continue to the maintenance treatment period if the investigator determines that the benefit of continued treatment outweighs the risk. During the maintenance treatment period, subjects will receive one more dose of the investigational drug (intratumoral injection to the lesion, tentatively scheduled for Day 1, the dosing regimen may be adjusted based on the PK characteristics of this study by the sponsor and investigator).

Early Termination/End of Treatment (EOT) Visit: This will be scheduled within 7 days after the decision to discontinue treatment. If the assessments required for the

EOT visit were performed within 7 days prior to the EOT visit, they do not need to be repeated.

Safety Follow-up: Subjects who have received at least one dose of the study drug will undergo a safety visit 28 days (± 3 days) after the last dose. If the assessments required for the safety visit were performed within 3 days prior to the safety visit, they do not need to be repeated.

Medical History and Treatment History: Collected during the screening period, including past medical history, medication history (concomitant treatments within 4 weeks prior to screening and currently ongoing), history of all previous tumors (including tumor stage, diagnosis date, genetic test results), history of all previous anti-tumor treatments, family history, surgical history, immunization history, allergy history, smoking history, alcohol history, history of drug abuse/dependence, etc.

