Vital Signs: Including respiratory rate, pulse/heart rate, blood pressure, and body temperature. Measured during screening, within 2 hours before CNSI-Fe administration, 1.5 hours (± 30 minutes) after administration, on Days 7, 14, and 21 of each cycle, at the End of Treatment (EOT) visit, and during the safety follow-up visit (excluding telephone visits).

Physical Examination: Including general condition, skin and mucosa, lymph nodes,

head, neck, chest, abdomen, spine, limbs, and nervous system. A complete physical examination will be performed during screening, before CNSI-Fe administration, at the EOT visit, and during the safety follow-up visit (excluding telephone visits). Symptom-directed physical examinations will be performed during the treatment period as clinically indicated.

Body Weight: Measured during screening and before CNSI-Fe administration.

ECOG performance status, complete blood count, urinalysis, blood chemistry, coagulation function, pregnancy test (for women of childbearing potential), and tumor marker tests should be completed within 7 days prior to the first dose of the investigational drug.

12-lead ECG: Performed during screening, within 2 hours before CNSI-Fe administration, 0.5 hours (± 5 minutes), 4 hours (± 30 minutes), 8 hours (± 30 minutes), 24 hours (± 30 minutes), 48 hours (± 30 minutes), and 72 hours (± 30 minutes) after administration, on Days 7, 14, and 21 of each cycle, at the EOT visit, and during the safety follow-up visit (excluding telephone visits). Continuous cardiac monitoring will also be performed for 8 hours after CNSI-Fe administration. Additional 12-lead ECG assessments may be added during the study to ensure subject safety, at the discretion of the investigator.

Echocardiography: Left ventricular ejection fraction (LVEF). Performed during screening, and as needed during the study period if there are clinically significant ECG abnormalities.

Concomitant Medications: All concomitant medications and treatments from the time of ICF signing until 28 days after the last dose or the start of a new anti-cancer therapy (whichever occurs first) should be recorded in the patient's medical records and reported in the electronic case report form (eCRF), including the name, reason for use, dose, route of administration, frequency, start date, and stop date.

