Adverse Events (AEs): Only serious adverse events (SAEs) related to the protocol-specified procedures should be reported before the start of study drug treatment. After the start of study treatment, all AEs should be reported, regardless of their relationship to the study drug, until 28 days after the last dose. The investigator should follow up on all AEs until the event resolves to baseline or better, is considered stable by the investigator, the subject is lost to follow-up, or the subject withdraws consent. For all SAEs related to the investigational product or study procedures, every effort should be made to follow up until a final outcome can be reported.

Blood routine: Red blood cell count (RBC), hemoglobin (Hb), hematocrit, white blood cell count (WBC) and differential count (neutrophils, eosinophils, lymphocytes, monocytes, basophils and others) and platelet count (PLT). To be performed within 7

days prior to first dose of study drug in the screening period, on Day 7, Day 14, Day 21 of each cycle, at the End of Treatment (EOT) visit, and at the safety follow-up visit (excluding telephone visits). Additional blood routine tests can be performed as needed based on the investigator's clinical judgment.

Urinalysis: Urine specific gravity, urine pH, urine glucose, urine protein, urine ketone, urine red blood cells and urine white blood cells. To be performed within 7 days prior to first dose of study drug in the screening period, on Day 7, Day 14, Day 21 of each cycle, at the EOT visit, and at the safety follow-up visit (excluding telephone visits).

Biochemistry: Glucose, blood urea nitrogen (BUN) or urea, creatinine (Cr), sodium, potassium, magnesium, chloride, calcium, phosphorus, total bilirubin (TBIL), alanine aminotransferase (ALT), aspartate aminotransferase (AST), alkaline phosphatase (ALP), lactate dehydrogenase (LDH), total protein, albumin, triglycerides, total cholesterol, amylase, lipase. To be performed within 7 days prior to first dose of study drug in the screening period, on Day 7, Day 14, Day 21 of each cycle, at the EOT visit, and at the safety follow-up visit (excluding telephone visits). Additional biochemistry tests can be performed as needed based on the investigator's clinical judgment.

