Coagulation function: International normalized ratio (INR), prothrombin time (PT), activated partial thromboplastin time (aPTT), thrombin time (TT), fibrinogen (FIB). To be performed within 7 days prior to first dose of study drug in the screening period,

on Day 7, Day 21 of each cycle, at the EOT visit, and at the safety follow-up visit (excluding telephone visits).

Pregnancy test: For female subjects of childbearing potential only; to be performed within 7 days prior to first dose of study drug in the screening period, at the EOT visit, and at the safety follow-up visit (excluding telephone visits). Pregnancy tests other than screening can be either serum or urine pregnancy tests, as per the investigator's judgment. If a urine pregnancy test is positive, it must be confirmed by a serum pregnancy test.

FSH test: For post-menopausal female subjects over 45 years of age but less than 55 years of age (see Section 4.1), a serum FSH test will be performed during the screening period to confirm post-menopausal status. If the subject is confirmed to be post-menopausal, no further pregnancy testing will be required; otherwise, she will undergo pregnancy testing like female subjects of childbearing potential.

Viral serology: Including hepatitis B virus (HBV) - [hepatitis B surface antigen (HBsAg), hepatitis B surface antibody (HBsAb), hepatitis B core antibody (HBcAb), hepatitis B e antigen (HBeAg), hepatitis B e antibody (HBeAb)], hepatitis C virus (HCV) - [HCV-Ab] and human immunodeficiency virus (HIV) - [Anti-HIV] testing.

HBV quantitative requirement: During screening, test the 5 HBV markers, if HBsAg is positive, HBV DNA testing is required; if HBsAg is negative but HBcAb is positive,

HBV DNA testing is also required. HCV quantitative requirement: During screening, test for HCV-Ab to determine if the subject has HCV infection, if HCV-Ab is positive, HCV RNA quantitative testing is required.

Iron tests: Serum iron (Fe), total iron binding capacity (TIBC), serum ferritin (SF), transferrin saturation (TSAT). To be performed during screening, within 24 h prior to CNSI-Fe dosing, at 5 min \pm 1 min, 15 min \pm 2 min, 30 min \pm 5 min, 2 h \pm 30 min, 6 h \pm 30 min and 10 h \pm 30 min post-dosing, on Day 7, Day 14, Day 21 of each cycle, at the EOT visit, and at the safety follow-up visit (excluding telephone visits). Additional iron tests may be performed as needed for subject safety during the study.

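### The schedule notes list no pregnancy test between the first dose and the maintenance injection, so the result at re-dosing can be about 21 to 28 days old, against a 7-day limit at dose 1

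*Combined protocol and SAP*

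**What the plan says.** For entry, the Inclusion Criteria in the synopsis require of women of childbearing potential that "a negative pregnancy test result must be obtained within 7 days prior to the first dose of the study drug". The Table 1-1 notes repeat this timing in a sentence covering a group of baseline tests: "pregnancy test (for women of childbearing potential), and tumor marker tests should be completed within 7 days prior to the first dose".

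The note on the pregnancy test itself gives its full list of times: "within 7 days prior to first dose of study drug in the screening period, at the EOT visit, and at the safety follow-up visit". It allows serum or urine tests after screening and requires serum confirmation of a positive urine test.

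Dosing does not end with the first injection. Under Study Period, "The DLT evaluation period is the first treatment cycle (duration: 21 days" is how the plan sets cycle 1. Subjects without unacceptable toxicity, and with a favourable benefit-risk judgement, then enter maintenance, where "subjects will receive one more dose of the investigational drug" (Table 1-1 notes, Maintenance Treatment Period). The Dosing Volume section also allows unplanned doses, and the section on study duration allows responders to continue on drug after the study ends.

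On the two later test times, the EOT note says "This will be scheduled within 7 days after the decision to discontinue treatment", and the Safety Follow-up note places that visit 28 days (± 3 days) after the last dose.

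**The concern.** The plan treats pregnancy as a bar to the first injection and requires a recent negative test to rule it out. The notes attach no such test to the second injection of the same drug, about three weeks later. A site that follows the notes exactly could re-dose a woman of childbearing potential in a first-in-human trial without a current result.

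The omission also stands out among the tests it is grouped with at baseline: the other laboratory tests in that group are repeated on Day 21 of each cycle. What is at stake is possible fetal exposure to the investigational drug. The statistical content of the trial is not touched.

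**Working it through.** The plan states no figure for the age of the pregnancy result at re-dosing, so there is none to reproduce. The check has three steps.

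**1. Does any listed test fall between dose 1 and dose 2?**

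- Screening test: before dose 1.
- EOT test: after the decision to discontinue treatment, so not before dose 2 in a woman who is going on to receive it.
- Safety follow-up test: 28 ± 3 days after the last dose, so after dose 2 in a woman who receives it.

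None of the three falls in the interval. The general note at the head of the Table 1-1 notes, that assessments are done on the dosing day before administration unless specified otherwise, governs when scheduled assessments happen. It does not add one, and the pregnancy test has its own specified times.

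**2. How old is the latest listed result at dose 2?**

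Inputs: the interval from test to dose 1 is 0 to 7 days (Inclusion Criteria); the DLT period is 21 days (Study Period); the Day 21 visit window is ± 1 day (Table 1-1 notes). No latest date for dose 2 appears in the text available.

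Age at dose 2 = (days from test to dose 1) + (days from dose 1 to dose 2)

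- Nominal timing: 0 + 21 = 21 days, to 7 + 21 = 28 days.
- Dose 2 given at the Day 21 visit, using its window: 0 + 20 = 20 days, to 7 + 22 = 29 days.
- Assumed 7-day delay: 0 + 28 = 28 days, to 7 + 28 = 35 days.
- With a test required within 7 days before dose 2: 0 to 7 days, the same as at dose 1.

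**3. How are the companion tests handled?**

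The sentence that groups baseline tests within 7 days of the first dose names six laboratory tests. Their individual notes give these repeats:

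- Blood count: "on Day 7, Day 14, Day 21 of each cycle, at the End of Treatment (EOT) visit".
- Urinalysis and biochemistry: "in the screening period, on Day 7, Day 14, Day 21 of each cycle, at the EOT visit", in the same words for both.
- Coagulation: Days 7 and 21 of each cycle.
- Tumor markers: Day 21 of each cycle.
- Pregnancy test: no within-cycle repeat.

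So 5 of the 6 are repeated on Day 21 and 6 − 5 = 1 is not. Performance status is in the same sentence but is not a laboratory test and is left out of the count.

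**The case against.** The strongest objection is that part of the plan is not visible. The visit-by-visit grid of Table 1-1 is missing from the text available, the notes break off, and later sections that the text cites are absent. Performance status shows that the notes do not carry every visit: it is a safety endpoint, yet no post-dose time for it appears in them. This stands as a limit: a further pregnancy test may be listed elsewhere. It does not remove the point, because performance status has no note of its own, whereas the pregnancy test has one that sets out its times. If the grid does list a further test, the note still needs to be aligned with it.

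Second, the comparison with the five repeated tests is only suggestive. They monitor toxicity or tumor response, while a pregnancy test is an eligibility and exposure check. Viral serology is not listed for repetition either, and echocardiography and cardiac enzymes are repeated only on clinical grounds. That is fair. The comparison shows a difference in handling, not an oversight, and the finding does not depend on it.

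Third, no rule is broken: the 7-day limit is written for the first dose only. This is correct. The point is a gap in protection, not a contradiction, and applying 7 days to dose 2 extends the plan's own standard.

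Fourth, other controls exist: highly effective contraception or abstinence, the benefit-risk judgement before maintenance, and a physical examination before administration. They reduce the risk, but none establishes pregnancy status. Contraception during treatment is an entry condition as well, and the plan still asks for a negative test before dose 1.

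Last, a responder who continues treatment after the safety follow-up visit would have had the test at that visit. The 21-to-28-day figure therefore does not carry over to such a dose, and no age is computed for it.

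**Conclusion.** The concern holds for the written schedule notes. No listed pregnancy test falls between dose 1 and the maintenance injection, and the latest listed result is about 21 to 28 days old if dose 2 is given when the 21-day DLT period ends. Each day of delay adds one day. The limit at dose 1 is 7 days.

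This rests on two assumptions: that dose 2 follows the DLT period directly, and that neither the unseen grid nor a later section adds a test. Confidence is moderate because of the second.

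The documents do not give the number of women of childbearing potential; they are a subset of at most 30 subjects. No probability of exposure in pregnancy is claimed. The change should be made on participant-safety grounds.

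**What to change.** First check whether the Table 1-1 grid or a later section already requires a test before dose 2; if so, bring the note into line with it. Otherwise amend the Pregnancy test note to require a negative result within 7 days before each further CNSI-Fe dose: the maintenance dose, any unplanned dose, and any continued dose in a responder. Urine is acceptable, with serum confirmation of a positive, as the note already provides. Test at the Day 21 visit where possible; if the next dose falls more than 7 days after that visit, test again before dosing. Keep the EOT and safety follow-up tests.

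The cost is one urine test per re-dosed woman of childbearing potential for each further dose, plus a serum test if it is positive. For the maintenance dose that is at most 30 urine tests (the enrolment cap), and fewer in practice because the trial enrols both sexes aged 18 to 80. No extra visit is needed when dose 2 follows within 7 days of the Day 21 visit, where urine is already collected. A longer gap means a repeat test before dosing.
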